Statistical Method per Outcome Specific Aim 1: Replicate Previous Favorable Behavioral Response to AAI Primary Main Outcome: Behavior responses. This parallel-group randomized design and will utilize a multi-method and multi-source assessment protocol. The assessment protocol will use a repeated-measure within-subject design, gathering main outcomes at three time points to assess the efficacy of AAI on outcomes for children with ADHD who are participating in a short-term intervention with or without the assistance of certified therapy dogs (see Figure 1). Our previous research indicated that after just 2 weeks of intervention, participants in the AAI condition showed significantly greater improvement in symptoms compared to control participants and that these gains were maximized by 10 weeks and then maintained at 6 weeks post intervention ([name] et al., 2018a), suggesting that 10 weeks is an ideal duration of treatment to detect significant benefits from AAI with dogs. Outcomes from AAI utilizing a manualized treatment with therapy dogs (AAI) will be compared to standard of care evidence-based psychosocial treatment at usual (control). Specific Aim 2: Determine Physiological Response over time to AAI for children with ADHD. Exploratory Main Outcome: Diurnal HPA and ANS responses. To determine if children with ADHD present with measurable changes in physiological responses to a short-term AAI (10 weeks) on measures of HPA and ANS we will gather candidate salivary analytes (salivary cortisol, uric acid, and alpha-amylase; Cort, sUA, sAA, respectively) and measures of cardiac rhythm, (heart rate variability; HRV) prior to and post intervention for children participating in both treatment conditions before, immediately after, and upon treatment follow up. Specifically, for each domain we will ascertain changes in diurnal patterns of candidate physiological measures utilizing a linear, repeated measures design gathered across three (3) points in time; establishing individual baseline patterns, end of treatment patterns, and then patterns at 6 weeks post-treatment. Specific Aim 3; Explore Individual Differences as potential mediators of response to AAI in children with ADHD. Secondary Outcome Exploratory Mediator Analysis; In the proposed study, we will explore how children's individual (a) acute physiological responses during intervention sessions and their individual (b) social interaction quality during intervention sessions may play a role in each of the Main Outcomes. Specifically, we will a) ascertain acute HPA activity (as measured by Cort, and sUA) and acute ANS activity (as measured by HRV and sAA) during intervention sessions across

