If appropriate describe secondary or post hoc analyses of primary outcome(s) or other exploratory analysis and if necessary, provide a breakdown of the methods used per outcome or endpoint:

Statistical Method to Inform Randomization Bias: Intent to treat bias. To establish equivalence of randomly assigned groups pre-intervention, t-tests will be performed on outcome measures comparing the groups. Means and standard deviations will be obtained and effect sizes calculated. Demographic profiles will be obtained and bivariate significant tests performed to assess the balance expected with randomization. Cohort effects on outcome as well as participation rates will be evaluated to assess any bias related to location, calendar time, or other session characteristics. Participation rates across the intervention will be tracked and compared between the randomized groups. In the spirit of the intent to treat principle (White, Carpenter, and Horton 2012) every effort will be made to conduct follow-up assessments on all randomized participants. Withdrawals will be documented with reason provided. In addition, multi-level modeling allows all cases to remain in a repeated measures model and will be done as a sensitivity analyses to primary analyses done on individuals with at least one follow-up point.

Sample Size Determination: Explain how the overall target sample size was determined (e.g., power analysis; precision estimation), providing justification of the effect size for the primary outcome based on preliminary data, current knowledge/literature and/or cost consideration; if appropriate, provide sample size justification for secondary outcomes. Power analysis should (at least) match the primary outcome/endpoint:

Sample Size. This exploratory study will employ a parallel-group randomized clinical trial design in which 48 participants will be randomly allocated to one of two (2) treatment/intervention groups (AAI and Control) delivered across four (4) cohorts in two (2) waves over the span of two (2) years ($n = 12$ per parallel ten-week cohort) in efforts to inform the specific aims of the study.

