Power & Expected Effect Size. Sample size analysis was conducted for randomized controlled design, using SAS PROC power. For the primary analysis of the main outcome domain (Aim 1: ADHD Behavior) with type I error rate of .05 was implemented for a repeated measures analysis evaluating group main effect, treatment main effect, as well as the group*treatment interaction. Effect size estimates from the authors' previous parallel-group randomized study of HAI demonstrated large AAI vs control effect size for problem behaviors (.86) and moderate effects on inattention (.45) ([name] et al., 2018a). For Aim 1, with a projected analysis of $n=48$, this exploratory study will exceed 90% power to detect effect sizes of .19 and above. At a level of 80% power, the minimum detectable effect was determined to be .21. For Aim 2, $n = 48$ will, for each of the two primary physiological outcome domains (Aim 2: Diurnal Pattern Hypothalamic Pituitary Adrenal axis activity; HPA and Autonomic Nervous System activity; ANS), a multilevel model will be constructed to assess pre-post intervention change, post-follow up change, group differences at each assessment, and group differences in degree of change. Models will account for within-subject correlation and within-cohort correlation. Four (4) cohorts of 13 participants each will be recruited for a total enrolled target sample size of 52 families over Years 1 and 2, accounting for an anticipated attrition rate of about 8% which is based on our recently completed study of AAI with ADHD ([name], et al., 2018a) in efforts to yield a total sample of 48.

Research Procedures

Provide a detailed chronological description of the clinical or treatment plan:

See Study Design

List all procedures involving the use and/or collection of photographs, or audio/video recording:
Facial image will be in video or photo Participants' first names may be collected or recorded in either video or audio recording

Specify the total duration of a subject's participation in the study and clearly outline the duration of participation for each study visit and sub-study, as applicable:

See Study Design

List data collection tools (e.g., measures, questionnaires, observational tool) below by clicking the 'Add Line' button. Include additional rows for study instruments, as needed:

The 'Columns' button allows you to display or hide columns in the Study Instrument List.

Name of Tool:

The Child's Sleep Habits Questionnaire (Owens, Spirito, & McGuinn 2000)

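### The Aim 1 detectable effects of .19 and .21 are not on a comparable scale with the prior effects of .86 and .45 beside them, so the power implied for .45 is not supported

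*Combined protocol and SAP*

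**What the plan says.** The sizing of Aim 1 is in Statistical Considerations, under Sample Size and Power & Expected Effect Size. The design is stated as "48 participants will be randomly allocated to one of two (2) treatment/intervention groups (AAI and Control"), and the Aim 1 methods text describes "gathering main outcomes at three time points to assess the efficacy of AAI". The error rate and model are given as "with type I error rate of .05 was implemented for a repeated measures analysis evaluating group main effect"; the full list of tests is "evaluating group main effect, treatment main effect, as well as the group*treatment interaction".

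The prior evidence comes next: the earlier trial "demonstrated large AAI vs control effect size for problem behaviors (.86) and moderate effects on inattention (.45"). The power claims follow directly: "this exploratory study will exceed 90% power to detect effect sizes of .19 and above", and "At a level of 80% power, the minimum detectable effect was determined to be .21".

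For neither pair of numbers does the section name the effect-size metric. It does not say which of the three listed tests was powered, whether the test is one- or two-sided, or what within-child correlation was assumed. Within-subject correlation is mentioned only for the Aim 2 models, without a value. Specific Aim 1 is to replicate the earlier behavioural findings.

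**The concern.** The four numbers are set out as if they could be compared: prior effects of .86 and .45, then detectable effects of about .2. Read that way, the trial has far more than 90% power for both prior effects. But a 48-child, two-arm trial does not normally detect a standardised difference of .2, so the two pairs are probably on different scales.

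Inattention is one of only two prior effects used to justify the sample size of a replication aim. If its real power is well below 90%, the paragraph gives the wrong background for interpreting an inattention result, and the wrong basis for the sample size that the progress report says the power analysis indicated.

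**Working it through.** **Inputs from the plan.** N = 48, two arms, alpha .05, three visits (one baseline, two later), prior effects .86 and .45, claimed detectable effects .19 (above 90% power) and .21 (80% power).

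**Assumptions, because the plan is silent.** 24 per arm; two-sided test; equal correlation r between any two visits; the same difference at both later visits; no clustering by cohort or session group.

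**Step 1. Try to reproduce .19 and .21.** No single scale and design gives both as printed, because the detectable effect must rise with power and here it falls. The closest match is Cohen's f for the group-by-visit interaction, with noncentrality f² × N × 3/(1 − r) on 2 and 92 degrees of freedom. At r = .5:
- f = .19: .0361 × 48 × 3/.5 = 10.4, power 82%.
- f = .21: .0441 × 48 × 3/.5 = 12.7, power 89%.
- Detectable f is .186 at 80% and .213 at 90%.

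This is the printed pair with the power levels exchanged. At r = .7, f = .19 has 96.5% power, so the plan's statement of more than 90% power at .19 can hold as f, but .21 then has about 99% power and is not the 80% detectable effect.

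**Step 2. Convert that f to a mean difference.** Let the arm difference be 0, d, d over the three visits. The mean difference is 2d/3, so the interaction deviations are −2d/3, d/3, d/3, split as half in each arm. Their mean square is (d²/9 + d²/36 + d²/36)/3 = d²/18, so f = d/√18 = 0.236d. Then .19 corresponds to d = .81 and .21 to d = .89. In the other direction, .45 becomes f = .106.

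**Step 3. Read .19 and .21 as mean differences.** Unadjusted two-sample t test, noncentrality d√(24/2), 46 degrees of freedom:

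| d | .19 | .21 | .45 | .86 |
|---|---|---|---|---|
| Power | 10% | 11% | 33% | 83% |

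The detectable d is 0.83 at 80% and 0.96 at 90%. By normal approximation, .19 at 90% needs 2(1.960 + 1.282)²/.19², or 583 per arm; .21 at 80% needs 2(1.960 + 0.842)²/.21², or 356 per arm. A one-sided test gives only 16% and 18% power for .19 and .21.

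**Step 4. Allow for the repeated measures.** Baseline adjustment multiplies the SD by √(1 − r²) at one follow-up, and by √((1 + r)/2 − r²) for the mean of two follow-ups (45 degrees of freedom).
- .21 at 80% power needs r = .97 (one visit) or .96 (mean of two).
- .19 at 90% power needs r = .98 or .97.

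**Step 5. Power for .45 as a mean difference.**

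| Analysis | r = .3 | r = .5 | r = .7 | r for 80% |
|---|---|---|---|---|
| Baseline-adjusted, one visit | 36% | 42% | 57% | .84 |
| Baseline-adjusted, mean of two follow-ups | 53% | 58% | 72% | .77 |
| Group-by-visit interaction, f = .106 | 25% | 34% | 52% | not computed |

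Reaching 90% with the two adjusted analyses needs r of about .88 and .83. For .86, the mean-of-two analysis has 97% power or more at every r from .3 upward.

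**The case against.** The strongest reply is that the inputs that decide the matter are not in the documents. The metric of .86 and .45 is inferred from their labels, and the source trial is not available here. If .45 were itself an f, power would exceed 90%. The within-child correlation is also unstated, and above about .77 to .84 an adjusted analysis reaches 80% power for .45. A change of scale does not by itself create a shortfall either: under the common two-group conversion f = d/2, .45 becomes .225, and interaction power at r = .5 is 93%.

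Part of this stands: the shortfall is conditional. But by the usual benchmarks an f of .45 would be called large, whereas the plan calls it moderate, and both labels suit a mean difference. The d/2 conversion belongs to a two-group main effect. In a randomised trial with equal baselines and the same difference at both later visits, the interaction f is d/√18.

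A reader might also infer that a non-significant inattention result is the more likely outcome even if .45 is real, or that it would be declared a failed replication. The documents support neither. With baseline adjustment on the mean of both follow-ups, significance is the more likely result at every r from .3 to .8. The plan sets no replication criterion, does not name inattention as the primary endpoint, and calls the study exploratory. That last label softens the consequence but does not cancel an explicit power claim; the remark that the study is not fully powered is attached to the mediation aim.

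**Conclusion.** The concern holds in conditional form. On the mean-difference scale that the prior effects appear to use, the .19 and .21 claims are not credible: about 10-11% power unadjusted, and a correlation of about .96 to .98 to reach the stated power. Exchanging the two numbers would repair their order but leave the scale problem.

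If .45 is a standardised mean difference, n=48 gives it about 33% power unadjusted and, for r between .3 and .7, from 25% (interaction test) to 72% (baseline-adjusted mean of both follow-ups). None of these supports the figure above 90% that the paragraph implies. The .86 effect is much better covered: 83% unadjusted, and 97% or more in the best of these analyses.

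The flat statement that 48 children cannot replicate .45 goes too far, because metric and correlation are unstated and a correlation near .8 would change the answer. All figures assume 24 per arm, a two-sided test, equal correlations and no clustering; clustering within cohorts or session groups would lower power further.

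**What to change.** Replace the two sentences giving .19 and .21. State the detectable effect at 80% and 90% power as an AAI-minus-control standardised mean difference, after confirming from the prior report that .86 and .45 are on that scale. Name the metric, the single tested effect that was powered, the sidedness and the assumed within-child correlation. Then tabulate power for .45 and .86 over a range such as r = .3 to .8 for the planned primary analysis. A single fixed percentage should not be substituted, because the answer depends on model and correlation. For orientation, under the assumptions above, the 80% detectable differences at r = .3, .5, .7 and .8 are 0.79, 0.72, 0.59 and 0.50 (baseline-adjusted, one visit) or 0.62, 0.58, 0.50 and 0.42 (baseline-adjusted mean of two follow-ups).

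Add that the inattention effect will be reported with its confidence interval set against .45, so that its compatibility with the earlier result can be judged directly.

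The cost is wording and a less favourable stated figure. Sample size, visits and procedures do not change. The progress report says that no data had been analysed at that point, so a correction made then would precede any results.

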Progress Report

UCI Progress

Please provide a detailed description of the progress of the study, including a brief summary of any interim findings or trends, and plans for the next approval period:

Initial participant recruitment and intervention was delayed by the pandemic, with the first eligibility visits starting in the fall of 2021. Recruitment, screening, eligibility visits, and intervention are presently ongoing. The targeted enrollment for this study is 48-52 participants, with 22 participants consented and found eligible for enrollment to date. A no-cost extension was filed with NIH, extending the research period to 8/31/2023 in an effort to complete recruitment of the targeted sample size indicated by power analysis. No data has been analyzed to date. Full enrollment is targeted for March of 2023, with intervention sessions ending by June, 2023. Data analysis, presentation and publication of findings are expect for Summer 2023.

Relying Entity Progress (as applicable)

If UCI is the IRB of Record for a non-UCI entity, provide a progress report for each relying entity (e.g., number of participants enrolled at the sub-site; data analysis performed, if any, etc):

N/A

Informed Consent

Confirm that there is no new information that raises concerns about the circumstances under which informed consent is being obtained:

No new information

Confirm that any new findings that have developed since the last continuing review, have been provided to enrolled subjects, as appropriate:

No new findings

Confirm that the research team is using the most recently approved version of the consent/assent document and that it contains the most accurate, up-to-date information about the research:

Yes

Confirm that all signed consent documents are on file and available for inspection:

Yes

Specify if any subjects were enrolled using a non-English consent document, information sheet, or script:

No

Given that some research studies have multiple consent/assent forms, please indicate which approved consent/assent forms should be reviewed by the IRB:

Review all consent/assent forms

Re-Consent Status

Are there approved Re-Consent Cover Memos on file?

IMPORTANT! To verify, review the 'Approved' documents in the Attachments section.

Yes

Is the re-consenting of participants complete?

Yes, all reconsenting is complete

REQUIRED! Review and review the Attachments section to remove all re-consent cover memos that are no longer being used.

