These amendments are to be tracked by the Lead Researcher independently. If the amendment changes the level of review to where IRB review is required, a new protocol must be submitted.

IRB Amendment

What **type of changes** are being proposed for this request?

Minor Revision(s)

Current Status of Enrollments:

Enrollment ongoing - research procedures ongoing

Number of subjects currently receiving active research intervention or if on hold, the number of subjects who were receiving active intervention prior to the hold.

8 subjects are actively engaged in research intervention at this time.

Re-consent

Are there approved Re-Consent Cover Memos on file?

IMPORTANT! To verify, review the 'Approved' documents in the Attachments section.

Yes

Is the reconsenting of participants complete?

Yes, all reconsenting is complete

REQUIRED! Review and review the Attachments section to remove all re-consent cover memos that are no longer being used.

Is there significant new information that would warrant notification or reconsenting of participants?

No

List of Protocol Changes

List all requested changes below and provide justification for the change, as applicable.

IMPORTANT! The list below must be complete / comprehensive of all changes as it will be reflected in the IRB Approval Letter. Failure to provide a complete list of changes will delay IRB approval.

Change in Consent

Provide the details and reason for the change in consent:

The approved consent form indicates participants will be paid by check but they will be paid in cash. The Informed Consent has been modified with tracked changes and will be attached.

Other Change(s)**Provide the details and reason for the other change(s):**

The approved Protocol Narrative indicates participants will be paid by check but they will be paid in cash. The Protocol Narrative has been modified with tracked changes and will be attached.

Confirmation of Changes:

Check here to confirm that all changes to the protocol are listed above

End of amendment form!**Project Details**

Specify the study title (**this title should not exceed more than 100 words**):

Animal Assisted Intervention with Dogs for Children with Attention Deficit/Hyperactivity Disorder: Exploring Candidate Physiological Markers of Response to AAI

Lead Researcher/Investigator:

[name]

Enter the Lead Unit:

IR-7462 - PEDIATRICS (Lead Unit)

Project Screener

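### Aim 1 power is stated only for 48 analysed children, a size that accrual to date makes doubtful, and the two power figures given for 48 contradict each other

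*Combined protocol and SAP*

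**What the plan says.** The Power & Expected Effect Size paragraph, under Statistical Considerations, gives Aim 1 power at a single size: "with a projected analysis of $n=48$, this exploratory study will exceed 90% power to detect effect sizes of .19 and above". The calculation is described as one "with type I error rate of .05 was implemented for a repeated measures analysis" covering group, treatment and interaction effects. The next sentence puts the minimum detectable effect at 80% power at .21. Effects of .86 (problem behaviours) and .45 (inattention) are cited from the team's previous randomised study. Four cohorts of 13 are planned, so 52 are enrolled and 48 remain after about 8% attrition.

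The Progress Report in the same document describes a pandemic-delayed start, "with the first eligibility visits starting in the fall of 2021". It continues: "The targeted enrollment for this study is 48-52 participants, with 22 participants consented and found eligible for enrollment to date". On timing it says "Full enrollment is targeted for March of 2023, with intervention sessions ending by June, 2023". It adds that a no-cost extension to 8/31/2023 was filed so that the sample size from the power analysis could be reached, and that no data have been analysed. The amendment form notes that "8 subjects are actively engaged in research intervention at this time". The renewal form reports no withdrawals or removals.

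The document gives no power figure below 48, and no statement of what follows if 48 is not reached.

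**The concern.** Aim 1 is a replication aim, so a non-significant result will be weighed against the power claimed in advance. The only claim available is for 48 analysed children. The count of 22 after roughly a year leaves that size in doubt, and the claim for 48 is itself self-contradictory. A reader of the final results could not tell from the plan what effect the trial was able to detect, at 48 or at any smaller size. The document's caution that the study is not fully powered is attached to the Aim 3 mediation analysis and not to Aim 1.

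**Working it through.** **1. The plan's own figures at 48.** Inputs from the power paragraph and study design: alpha .05, N = 48, two groups, three time points. Assumed because not stated: two-sided test, 24 per arm, children independent.

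- Read as a standardised mean difference (two-sample noncentral t), .19 gives about 10% power and .21 about 11%. This is not the metric used.
- Read as Cohen's f for the group-by-time interaction, the noncentrality is f² × N × m / (1 − ρ), with m = 3 visits, and degrees of freedom are m − 1 and (N − 2)(m − 1):

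| ρ | Power at .19 | Power at .21 | Effect at 80% | Effect at 90% |
|---|---|---|---|---|
| 0.5 | .818 | .891 | .186 | .213 |
| 0.6 | .898 | .949 | .166 | .191 |
| 0.7 | .965 | .987 | .144 | .165 |

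Power rises with effect size at fixed N, so no choice of ρ gives over 90% at .19 together with 80% at .21. At ρ = 0.5 the detectable effects are .186 (80%) and .213 (90%), which suggests that the two labels may have been swapped. That is a conjecture, since it depends on an assumed metric and correlation.

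**2. Attrition.** 52 × 0.92 = 47.8, consistent with 48.

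**3. Accrual pace.** The date of the count is not stated; 19 October 2022 is assumed from the date on the attached approval letter. The fall 2021 start is taken as 1 September to about 20 December 2021.

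- Observed: 22 / 13.6 months = 1.62 per month, to 22 / 10.0 = 2.20 per month.
- Time left: 4.4 months (1 March 2023) to 5.4 months (31 March).
- Needed for 52: 30 / 5.4 = 5.56 per month, to 30 / 4.4 = 6.82 per month.
- Ratio: 5.56 / 2.20 = 2.5, to 6.82 / 1.62 = 4.2.
- Needed for only 48 enrolled (enough if nobody drops out): 26 / 5.4 = 4.81 per month, to 26 / 4.4 = 5.91 per month, or 2.2 to 3.6 times the observed pace.

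**4. Final size under different assumptions.**

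| Scenario | Enrolled | Analysed |
|---|---|---|
| Straight line, low: 22 + 1.62 × 4.4 | 29.1 | × 0.92 = 26.8 |
| Straight line, high: 22 + 2.20 × 5.4 | 33.9 | × 0.92 = 31.2 |
| 22 came from two cohorts; two more of that size | 44 | × 0.92 = 40.5 |
| 22 came from two cohorts; two more of 13 | 48 | × 0.92 = 44.2, or 48 with no loss |

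The cohort rows are assumptions, because the number of cohorts completed is not reported.

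**5. Power across those sizes.** Unadjusted two-group t-test, noncentrality d × √(N/4), N − 2 degrees of freedom, with .86 and .45 taken as mean differences:

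| Analysed | Power, .86 | Power, .45 | Detectable d at 80% |
|---|---|---|---|
| 48 | 83% | 33% | 0.83 |
| 44 | 80% | 31% | – |
| 40 | 76% | 28% | – |
| 36 | 71% | 26% | 0.96 |
| 30 | 62% | 22% | 1.06 |
| 28 | 59% | 21% | 1.10 |

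These are conservative for an analysis that uses the baseline visit. Adjusting for a baseline correlated .5 with outcome turns .86 into .86 / √(1 − .25) = .993; with N − 3 degrees of freedom, power is about 71% at 28 and 75% at 30. On the interaction scale, power at f = .19 with 28 to 30 analysed is .56–.60 for ρ = 0.5, .67–.70 for ρ = 0.6 and .80–.83 for ρ = 0.7. Each is below its value at 48 in step 1.

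**The case against.** The power paragraph is a design-stage statement, conditional on 48 analysed, and slow accrual does not contradict it. The sponsor disclosed the count and obtained time through the extension. Accrual is by cohort, with assessment and randomisation inside a 21-day window before treatment, so a monthly rate predicts poorly. Nobody has withdrawn, and the primary analysis needs only one follow-up point, so 8% may overstate the loss. The study calls itself exploratory.

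Most of this stands, and it rules out three stronger readings that a reader might infer.

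- *That the stated power will not be delivered.* The documents do not show this. Enrolment was continuing, and the cohort scenarios reach 40 to 48 analysed.
- *That the trial has about 60% power.* That figure needs both the straight-line projection and an unadjusted single-visit test. The planned analysis is repeated-measures.
- *That over 90% at .19 is sound at 48 and only accrual undermines it.* The next sentence of the plan contradicts the figure before accrual enters.

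Nor does any passage say that a null result would be reported as a failed replication.

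The objection does not remove the need for a change. Counting from the first eligibility visit already leaves out the delay before that visit, and the amendment lists only a change from check to cash payment, with no new recruitment method or site. In the cohort scenarios, 48 analysed requires two full further cohorts and no attrition, while the plan itself allows for 8%. The extension is a response to the shortfall, but it does not supply a power figure for a smaller sample.

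**Conclusion.** The point holds in two parts. First, the Aim 1 power statement for 48 is internally impossible and cannot be reproduced without a metric and correlation that the plan omits; this does not depend on accrual. Second, 48 analysed by the stated dates is doubtful. The plausible range is about 27 to 48, and the plan gives power only at the top of it. For an effect of .86 read as an unadjusted mean difference, that range takes power from 83% at 48 to 59–62% at 28 to 30, with less loss under baseline or repeated-measures adjustment. For .45, power is low throughout (33% down to 21–22%). The accrual part rests on an inferred count date, an imprecise start date and an unreported number of completed cohorts. The power figures rest on equal arms, a two-sided test and independent children.

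**What to change.** In the Power & Expected Effect Size paragraph:

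1. Correct the statement for 48 analysed. Name the effect-size metric, the test being powered, its sidedness and the assumed within-child correlation, and make the 80% and 90% figures consistent.
2. Replace the single claim with a table of power (for .86 and .45, on a stated metric) and 80%-power detectable effect across about 28 to 48 analysed. The table in step 5 of the working can serve as the unadjusted version, with the planned repeated-measures analysis beside it.
3. State that recruitment closes on the calendar, without looking at outcome data. The Progress Report says none have been analysed, so this can still be fixed in advance.
4. State that Aim 1 will be reported as an estimate with its 95% confidence interval, set against the prior .86 and .45, whatever the final size, and that a non-significant result will not by itself be called a failure to replicate.

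The cost is a recomputed table and some wording, with no extra children, visits or staff. The downside is a less favourable stated power.

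### The two Aim 1 power figures contradict each other: more than 90% power at an effect of .19, but only 80% power at .21, with the same n = 48 and alpha of .05

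*Combined protocol and SAP*

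**What the plan says.** The figures are in the paragraph on power and expected effect size, under Sample Size Determination in the Statistical Considerations section. The Aim 1 calculation "with type I error rate of .05 was implemented for a repeated measures analysis", which is described as "evaluating group main effect, treatment main effect, as well as the group*treatment interaction". For Aim 1, with 48 participants projected for analysis, "this exploratory study will exceed 90% power to detect effect sizes of .19 and above". The sentence that follows reads: "At a level of 80% power, the minimum detectable effect was determined to be .21".

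The second sentence brings in no new sample size, alpha, outcome or test. The paragraph also cites effects of .86 (problem behaviours) and .45 (inattention) from the group's previous randomised study, without giving a scale. It plans to enrol 52 families so that 48 remain after about 8% attrition.

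The UCI Progress entry of the Progress Report relies on this calculation. It explains the no-cost extension as an effort to "complete recruitment of the targeted sample size indicated by power analysis".

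**The concern.** With the test, sample size and alpha fixed, power rises with effect size. The effect detectable with 80% power must therefore be smaller than the effect detectable with 90% power. The plan prints the reverse order, and so gives the single value .21 both more than 90% power and 80% power.

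These are the only numerical power statements in the documents. The Aim 2 text gives no power figure, and the mediation analysis is described as not fully powered. As printed, a reader cannot tell what effect on the primary aim the trial can detect, although the target sample size is attributed to this analysis.

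**Working it through.** **Inputs from the plan.** N = 48 analysed, alpha .05, two groups, main outcomes at three time points, and the two statements (above 90% at .19; 80% at .21). Not stated: sidedness, which of the three effects is powered, the effect-size metric, and the within-subject correlation.

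**Step 1. Order.** No calculation is needed. The value .21 falls within the range covered by the first sentence, so its power exceeds 90%. The second sentence gives it 80%. Both cannot hold for one test.

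**Step 2. Size of the conflict, with no correlation assumed.** For an F test, power = P[F′(df1, df2, λ) > F(.95; df1, df2)], where λ is the noncentrality. Two cases span a 2-df interaction over three assessments and a 1-df test:

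| df | λ for 80% | λ for 90% |
|---|---|---|
| 2, 92 | 9.955 | 13.076 |
| 1, 46 | 8.190 | 10.965 |

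With the design fixed, λ is proportional to e² if the effect e is Cohen's f or d, to e if it is f-squared, and to e/(1−e) if it is eta-squared. Unknown constants, including the correlation, cancel when moving from one effect to the other.

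Worked example (f or d; df 2, 92):
- Take 80% at .21 as right. At .19, λ = 9.955 × (.19/.21)² = 8.149, which gives power .711. The 90% detectable effect is .21 × √(13.076/9.955) = .241.
- Take 90% at .19 as right. At .21, λ = 13.076 × (.21/.19)² = 15.97, which gives power .950. The 80% detectable effect is .19 × √(9.955/13.076) = .166.

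Over both df cases and all three metrics:

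| Statement taken as right | Implied power at the other effect | Implied detectable effect |
|---|---|---|
| 80% at .21 | .711 to .760 at .19 (plan: above .90) | 90%: .241 to .281 (plan: .19) |
| 90% at .19 | .926 to .950 at .21 (plan: .80) | 80%: .142 to .166 (plan: .21) |

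The second row uses exactly 90%. The plan says more than 90%, which would only widen the gap. A one-sided normal approximation on the f or d scale falls inside the same ranges: power of 73% at .19 in the first case, and an 80% detectable effect of .161 in the second.

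**Step 3. Attempt to reproduce the plan's figures.** This step needs assumptions that the plan does not state: Cohen's f, the 2-group by 3-assessment interaction, and a within-subject correlation ρ. Then λ = 48 × 3 × f²/(1−ρ), with df 2 and 92.

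| ρ | 80% detectable f | 90% detectable f | Power at .19 | Power at .21 |
|---|---|---|---|---|
| .3 | .220 | .252 | .668 | .760 |
| .4 | .204 | .233 | .739 | .825 |
| .5 | .186 | .213 | .818 | .891 |
| .6 | .166 | .191 | .898 | .949 |
| .7 | .144 | .165 | .965 | .987 |

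No row gives both printed statements. Power at .19 reaches 90% at ρ = .602; power at .21 equals 80% at ρ = .362. Near ρ = .5 the pair resembles the printed numbers in the opposite order. So does a two-assessment test at ρ = .6 (.185 and .214). Swapped labels are therefore possible but not established.

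**Step 4. Reading the figures as Cohen's d.** For a plain comparison of two means with 24 per arm (1:1 assumed, two-sided), power is 9.6% at .19 and 10.9% at .21. The 80% and 90% detectable effects are .826 and .956. This reading supports neither statement.

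**The case against.** The strongest reply is that the ordering argument applies only within one test and one metric, and the paragraph names three effects without tying either figure to any of them. Mixed readings that fit can be constructed. An R-squared of .19 with 1 df has about 91% power, and an f-squared of .21 with 2 df about 79%. The contradiction is therefore not proven in the strictest sense. That is correct, but nothing in the text signals a change of test or metric between two adjacent sentences about the same aim. If two tests were meant, the text still has to say so.

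A second reply is that little depends on the figures. The study is called exploratory, no decision rule uses .19 or .21, and the earlier effects of .86 and .45 exceed even the largest 90% detectable effect in Step 2 (.281). This comparison helps only if all the numbers share one metric, which is not stated. Read as d with 24 per arm, .45 would have 34% power and .86 would have 85%. The point that stands is that this is an unverifiable power statement, not a demonstrated shortfall.

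Third, the table in Step 3 rests on assumptions outside the documents. That is also correct. It shows why the wrong figure cannot be identified, and the conclusion does not depend on it.

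**Conclusion.** The concern holds. For Aim 1 at n = 48 and alpha .05, the two printed figures are incompatible under any single test, whatever the metric, sidedness or correlation. The only assumption is that both sentences describe the same test and metric, which is how they read. The gap is material: either power at .19 is 71–76% instead of above 90%, or the 80% detectable effect is .14–.17 instead of .21. The documents do not show which figure is wrong or whether the labels were exchanged. Whether 48 is an adequate target is also unknown until the calculation is checked.

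**What to change.** Retrieve the original power output, or re-run it at 48 analysed. Replace the two sentences with a consistent pair in which the 80% detectable effect is below the 90% one. State alongside it:
- which effect is tested (group, treatment, or their interaction);
- the effect-size metric, and whether the cited .86 and .45 are on the same scale;
- the number of assessments, sidedness and within-subject correlation used.

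If the figures do come from different tests, label each one. Exchange the two labels only if the investigators' own output confirms it.

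The cost is one calculation and two corrected sentences. The correction itself changes no enrolment. The Progress Report records 22 participants enrolled and no data analysed, so it can be made before any results are seen.
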